5.2. Treatment Arms and Duration

Two treatment arms will be employed for the study:

- FF/VI 100/25 mcg QD via ELLIPTA + Placebo BD via Diskus
- FP 250 mcg BD via Diskus + Placebo QD via ELLIPTA

As this is a 2-period cross-over study, all randomized subjects will receive both treatments in the study either in Treatment Period 1 or Treatment Period 2. Also, each subject will receive a Diskus and ELLIPTA inhaler in Treatment Period 1 and Treatment Period 2.

Subjects will complete a 4-week single blind run-in on FP 250 mcg twice daily, followed by 2-week double-blind Treatment Period 1 on randomized treatment, a 2-week single blind washout period on FP 250 mcg twice daily, 2-week double-blind Treatment Period 2 receiving the alternative treatment, and follow-up contact approximately 7-days after completing Treatment Period 2. The total duration of study participation is approximately

11 weeks; and up to 15 weeks for subjects with SAR at screening who may need to be treated with intranasal corticosteroids followed by repeat screening visit.

5.3. Type and Number of Subjects

Subjects must have been diagnosed with persistent asthma with evidence of EIB and have been using a low- to moderate-dose ICS as a part of their asthma maintenance treatment. Assuming a 20% screen failure rate and 70% run-in failure rate, approximately 275 subjects will be screened in order to randomize 66 subjects in this study and ultimately achieve 56 evaluable subjects who have completed both the exercise challenges and spirometric evaluations at the end of both treatment periods. This calculation assumes a 15% withdrawal rate during the study.

5.4. Design Justification

The study design is based on the practice parameters for assessing EIB developed by the Joint Task Force on Practice Parameters for Allergy and Immunology [[Weiler, 2010](#)], American Thoracic society clinical practice guideline [[Parsons, 2013](#)], EMA (European Medicines Agency) Note on Guidance on Clinical Investigation of Medicinal Products for Treatment of Asthma [[EMA, 2013](#)] and FDA Draft Guidance for the Development of Drugs for Exercise-Induced Bronchospasm [[FDA Guidance for Industry, 2002](#)].

A randomized, double-blind, double dummy, cross-over design is a well-validated means to assess the efficacy and safety of two treatment groups. A cross-over design was chosen to reduce the impact of confounding variables, and allow for between and within group comparisons. The expectation that mild to moderate patients with EIB would already be using an ICS necessitated standardization of baseline ICS therapy and eliminates the need for use of a placebo comparator. Considering a 4-week run-in period on FP, two weeks of treatment with FF/VI followed by exercise challenge is considered adequate to observe a treatment effect for this within-subject comparison. A two-week washout period is adequate to wash out the LABA, VI, prior to Treatment Period 2.

FP was chosen as the “gold standard” ICS active comparator as its ability to prevent EIB has been previously characterized and FF is not currently commercially available outside of the US.

The primary endpoint of maximal percent decrease from pre-exercise baseline FEV₁ is a well-established measure of EIB and is consistent with agency guidance and established practice parameters. Exercise challenge testing at 12, and 23 hours post-dose at the end of each Treatment Period will allow for assessment of the duration of protective effect for the interventions.

5.5. Dose Justification

The inhaled FF/VI 100/25 mcg dose combination corresponds to the dose approved in the US (adults) and EU (adults and adolescents) for the treatment of asthma corresponding to low to moderate ICS/LABA asthma therapy. FF100 is deemed a low/mid strength ICS.

5.6. Benefit: Risk Assessment

Summaries of findings from both clinical and non-clinical studies conducted with FF (GW685698)/VI (GW642444) can be found in the corresponding Investigator's Brochure and in the RELVAR/BREO™ ELLIPTA Prescribing Information for countries in which FF/VI is approved for marketing. For the FP section, information is taken from the label of FLOVENT ACCUHALER/DISKUS.

The following section outlines the risk assessment and mitigation strategy for this protocol:

5.6.1. Risk Assessment

For FF/VI the following risks and the mitigation strategy as applicable to asthma patients were taken from the summary of safety concerns in the European Union – Risk Management Plan (EU-RMP). For FF/VI the data/rationale for the risk were derived from the 2014 Investigator's Brochure, from an integrated analysis of key RELVAR studies (Integrated Summary of Safety for Fluticasone Furoate/Vilanterol v02 DBL 31 Jan 2014), from the RMP version 6.2 and in the RELVAR/BREO ELLIPTA Prescribing Information for countries in which FF/VI is approved for marketing.

Potential Risk of Clinical Significance	Summary of Data/Rationale for Risk	Mitigation Strategy
Investigational Product (IP) [FF/VI]		
Pneumonia in patients with asthma	
The incidence of pneumonia in patients with asthma was uncommon. The incidence (adjusted for exposure) seen with FF/VI 100/25 microgram strength (8.5/1000 patient years) was similar to placebo (9.3/1000 patient years). No risk factors were identified.
 
In an analysis performed on the 18 key studies in subjects with asthma pneumonia was reported by 0.5% (13 of 2369) of subjects who received FF/VI 100/25 subjects and 0.2% (2 of 1070) of subjects who received placebo.^a
	
The risk of pneumonia in asthma patients is very low and is consistent with the risk of other ICS. Subjects are not at an increased risk in this study, since they enter the study stable on an existing ICS treatment. Subjects are alerted to the potential risk of pneumonia in the informed consent. Investigators are informed of the risk in Section 1.2.3 (Asthma Clinical Studies) and Section 5.3.3 (Safety in Asthma Clinical Studies) of the IB. Subjects with concurrent respiratory disease are excluded from the study.

Asthma related intubations and deaths	
This is a class effect of LABA in asthma. This has not been observed for FF/VI.
 
An FDA meta-analysis of LABA vs. no LABA (60,954 patients in 110 trials) by age group on a composite endpoint of asthma-related deaths, intubations, and hospitalizations (asthma
	
Subjects with a history of life-threatening asthma are excluded from the study.

Potential Risk of Clinical Significance	Summary of Data/Rationale for Risk	Mitigation Strategy
	
composite index) showed a statistically significant difference among age groups. The composite event incidence difference for all ages was 6.3 events per 1000 patient-years (95% confidence interval [CI]: 2.2-10.3) with LABAs compared with no LABA use. Among the 15,192 patients with concurrent ICS use, the incidence difference was 0.4 events per 1000 patient-years (95% CI: -3.8 to 4.6). The authors noted a trend of greater excess risk with LABA among the younger age groups [McMahon, 2011].
	
Serious cardiovascular events	
In an analysis performed on the 18 key studies in subjects with asthma, eight serious cardiovascular events have been reported in patients exposed to FF/VI. Seven events in FF/VI 100/25 and one event in FF/VI 200/25. This represents an incidence less than 1% in the asthmatic patients exposed to FF/VI.^a
 
The events reported include atrial fibrillation, acute coronary syndrome, coronary artery disease, hypertension, myocardial ischemia, tachyarrhythmia and tachycardia.
	
Subjects with existing serious cardiovascular disease and/or abnormal ECG findings are excluded from the study. Investigators are made aware of the potential class effects of LABAs and are advised to exercise caution for subjects with existing serious cardiovascular disease (Section 6.3 [Warnings and Precautions] of the IB).

Hypersensitivity	
No FF/VI drug related hypersensitivity was noted in clinical trials.
 
Spontaneous reports of hypersensitivity reactions have been reported in post-marketing
	
Subjects will be informed about the risk of hypersensitivity in the informed consent. Subjects will be advised to seek medical treatment if any signs of hypersensitivity occur.
 
Subjects with milk protein allergy or known

Potential Risk of Clinical Significance	Summary of Data/Rationale for Risk	Mitigation Strategy
	
data for FF/VI. A possible causal association cannot be ruled out based on the temporal association between drug administration and hypersensitivity events including anaphylactic reaction, angioedema, urticaria, pruritis and rash.
	
hypersensitivity to FF, VI, the classes ICS or beta-agonist or any ingredient of the IP preparation will be excluded from participating in the study. Investigators are informed of the risk in Section 6.2 (Contraindications) of the IB.


Decreased bone mineral density and associated fractures
	
Risk of fracture has been associated with oral corticosteroids. It is unclear if inhaled corticosteroids carry the same risk.
 
There were few events associated with bone disorders or fractures reported during the asthma development program. These events tended to be those associated with trauma.
 
Currently the risk of reduced bone mineral density has not been observed in the asthma population [Jones, 2002]. In addition specific assessments in adolescents with asthma have not demonstrated an effect on bone mineral density, when controlled for growth [König, 1993; Turpeinen, 2010].
 
In an analysis performed on the 18 key studies in subjects with asthma bone fractures were reported by <1% (16 of 2369) of subjects who received FF/VI 100/25.^a
	
Subjects will be informed about the risk of decreased bone mineral density and bone fractures in the informed consent. Investigators are made aware of the potential for this ICS class effect. Subjects will be advised to seek medical treatment if any signs of decreased bone mineral density or fractures occur.

Potential Risk of Clinical Significance	Summary of Data/Rationale for Risk	Mitigation Strategy
Adrenal Suppression	
This is considered a class effect of ICS. Preclinical studies showed that FF effects are comparable with other corticosteroids. No studies have shown a clinically relevant effect of FF/VI on the hypothalamic-pituitaryadrenal axis (HPA) at the 100/25 strength. This includes a formal HPA study (HZA106851), using 24-hour serum cortisol measurements, and multiple studies with chronic obstructive pulmonary disorder (COPD) and asthma subjects which monitored urinary cortisol.
	
Subjects will be informed about the risk of adrenal suppression in the informed consent. Investigators are made aware of the potential for this class effect in Section 6.3 (Warnings and Precautions) of the IB. If systematic symptoms appear, investigators should implement an appropriate treatment while observing the subject's' asthma symptoms.

Corticosteroid associated eye disorders	
This is considered a class effect of ICS. Preclinical studies showed FF at high dose comparable to other high dose corticosteroids. In study HZA106839 (FF/VI, FF and FP in subjects with asthma), formal ophthalmic assessments were conducted (including LOCS III evaluations for ocular opacities) throughout the study. This study showed no apparent effects on lens opacification, compared to baseline. During studies in both subjects with asthma and COPD, no associated affect on ocular disorders was observed.
	
Subjects will be informed about the risk of corticosteroid associated eye disorders in the informed consent. Subjects will be advised to seek medical treatment if any signs of eye disorder occur. Investigators are made aware of the potential for this class effect in Section 5.3.3.7 (Ophthalmic Effects) of the IB.

Study Design and Procedures		
Exercise-induced bronchoconstriction following exercise challenge testing	This study specifically recruits a study population which demonstrates a minimal level of exercise-	Exercise challenges may be stopped at any time during the assessment for worsening asthma. (Guidelines for treatment are provided in the

Potential Risk of Clinical Significance	Summary of Data/Rationale for Risk	Mitigation Strategy
	induced bronchoconstriction ($\geq 20\%$ decrease from their pre-exercise FEV ₁). However, more severe bronchoconstriction is possible following exercise challenge testing.	
study reference manual [SRM].)
 
If a subject's FEV₁ decreases to $\geq 40\%$ from their pre-exercise FEV₁ following exercise challenge, he/she must receive rescue therapy. If he/she requires rescue therapy with anything other than MDI (Metered Dose Inhaler) or nebulized albuterol/salbutamol or ipratropium (secondarily) following the exercise challenge assessment, he/she will not be allowed to continue in the study.
 
Subjects will be monitored until their FEV₁ reaches $\geq 95\%$ of their pre-exercise FEV₁. Rescue Albuterol/salbutamol may be given during recovery.

Cardiovascular stress resulting from exercise	Rigorous exercise can lead to heart attack, stroke and even death.	Subjects with existing serious cardiovascular disease and abnormal ECG findings are excluded from the study. Investigators are made aware of the potential class effects of LABAs and are advised to exercise caution for subjects with existing serious cardiovascular disease (Section 6.3 [Warnings and Precautions] of the IB).
Musculoskeletal injury resulting from exercise challenge testing	Musculoskeletal injury is a risk of exercise on a treadmill.	The exercise challenge will begin gradually to allow the subject to warm up over 2 minutes, and end with a gradual stop.
Falls or other injuries resulting from exercise	Exercise challenge testing will be conducted on a	Front and side handrails will be in place in order to prevent a fall. Subjects will be instructed to

Potential Risk of Clinical Significance	Summary of Data/Rationale for Risk	Mitigation Strategy
challenge testing	treadmill, with an air mask and heart rate monitor. Subjects unfamiliar with treadmill usage or with wearing equipment while on the treadmill could become unbalanced and fall.	refrain from holding on to the support railings during the challenge. At least one staff member will be behind and within reach of the subject throughout the challenge. It is recommended that 3 staff members should facilitate the challenge procedures.
Unknown risks to an embryo, fetus (unborn baby) or nursing infant	There are no studies with FF/VI or the individual components (FF and VI) in pregnant women.	
As specified in the protocol:
 
 • Women who are pregnant, lactating or are planning on becoming pregnant during the study are not eligible to participate in this study. • Female subjects must be postmenopausal or using a highly effective method for avoidance of pregnancy while in this study. • If a female subject becomes pregnant during the study, she should let the study doctor know immediately. The study medication will be stopped. • For women of child-bearing potential, a urine pregnancy test will be performed at Screening (Visit 1). For enrolled subjects, a urine pregnancy test will be performed at Screening, randomization, Visit 4 and at home at the Follow-Up contact. The result will be reported to the site study staff during the

Potential Risk of Clinical Significance	Summary of Data/Rationale for Risk	Mitigation Strategy
		Follow-Up Phone Contact.
Asthma symptoms may worsen during the study	
As specified in the protocol:
 
 • The use of certain asthma medications is excluded prior to and during the study. • After Visit 1, the use of rescue medication (albuterol/salbutamol) must be withheld for at least 6 hours prior to and during each clinic visit. • Patients will be placed on an ICS alone treatment during the run-in period and possibly during the treatment period. 	
The informed consent advises the subject to:
 
 • Talk to the study doctor about the excluded medications before deciding and consenting to participate in the study. • Use the rescue medication (albuterol/salbutamol) if asthma symptoms worsen. • Notify the study doctor or staff if his/her asthma symptoms worsen or do not get better after using the rescue medication. • Go immediately to the emergency department/seek medical attention if the symptoms are severe.
Shortness of breath, coughing, lightheadedness or fainting, and/or chest tightness during the spirometry measurements	None.	As specified in the informed consent form for this study, if any of these symptoms should happen to the subject, he/she will receive medical treatment.

a. RELVAR studies summarized include FFA109684, FFA109685, FFA109687, B2C109575, HZA106827, HZA106829, HZA113091, HZA113714, HZA113719, HZA116863, HZA106837, HZA106839, HZA106851, FFA112059, FFA114496, FFA115283, FFA115285, B2C112060.

5.6.2. Risk assessment for FP 250mcg

FLOVENT/FLIXOTIDE is a marketed drug that contains the ICS fluticasone propionate (FP 250 mcg). A similar profile of undesirable effects as reported for ICS may occur with FP. Since FLOVENT/FLIXOTIDE contains an ICS (FP), the risk mitigation strategies for FF (ICS) as mentioned in Section [5.6.1](#) will be applicable.

Please refer to the authorized product label for further information about the risks of using FP. In this study, FP will be used in line with the recommendations provided in the product label.

5.6.3. Benefit Assessment

Combined treatment with ICS and LABA has been shown to be more effective than the individual components in asthma, leading to the development of fixed dose combination inhalers. The use of ICS/LABA combinations is now well established in international treatment guidelines for moderate to severe persistent asthma patients for whom treatment with ICS alone is not sufficient.

In patients with persistent asthma, improvements in protection from EIB with ICS/LABA combination product FP/salmeterol (Advair) have been demonstrated [[Murray, 2011](#); [Pearlman, 2009](#); [Weiler, 2005](#)]. Once-daily FF/VI 100/25 mcg is hypothesized to provide protection from EIB throughout the dosing period.

FP 250 mcg is a commercially available product for the treatment of persistent asthma and has a recognized safety profile.

5.6.4. Overall Benefit: Risk Conclusion

GlaxoSmithKline (GSK) has assessed this study for any potential risks that a subject may experience. The investigational product (IP) FF/VI has an acceptable safety profile for clinical use and there are no significant associated risks. This conclusion is supported by the results of previously performed clinical studies with the products in healthy volunteers and subjects with Asthma and COPD. The ICS (FP) described above will be used at a dose and frequency that is approved for the treatment of Asthma and has an acceptable safety profile for use. This conclusion is supported by the results of previously performed clinical studies and post-marketing experience (see local label).

Adverse effects that could be associated with the use of FF/VI and FP will be closely monitored. A safety criterion outlining details for subject withdrawal is included in the protocol (Section [6.4](#), Withdrawal Criteria). A thorough summary and evaluation of the available pre-clinical data can be found in the IB. Routine safety analysis of this study will be conducted by the company.

Taking into account the measures taken to minimize risk to subjects participating in this study, the potential risks identified in association with FF/VI and FP are justified by the anticipated benefits that may be afforded to patients with asthma.

6. SELECTION OF STUDY POPULATION AND WITHDRAWAL CRITERIA

Specific information regarding warnings, precautions, contraindications, adverse events, and other pertinent information on the GSK investigational product or other study treatment that may impact subject eligibility is provided in the product label or IB/IB supplement(s).

Deviations from inclusion and exclusion criteria are not allowed because they can potentially jeopardize the scientific integrity of the study, regulatory acceptability or subject safety. Therefore, adherence to the criteria as specified in the protocol is essential.

6.1. Screening Criteria

6.1.1. Inclusion Criteria

A subject will be eligible for inclusion in this study only if all of the following criteria apply:

1. **Informed consent:** Subjects must give their signed and dated written informed consent to participate prior to commencing any study related activities.
2. **Age Range:** 12 to 50 years of age, inclusive, at Visit 1 (Screening).
3. **Diagnosis:** A diagnosis of asthma, as defined by the National Institutes of Health [NIH, 2007], for at least 12 weeks prior to Visit 1.
4. **Asthma Severity:** Subjects must have a pre-bronchodilator FEV₁ of $\geq 70\%$ of the predicted normal value. Predicted values will be based upon Global Lung Function Initiative (GLI) [Quanjer, 2012] equations for spirometry reference values.
5. **Evidence of EIB:** Subjects must answer “Yes” to at least 2 of the following 3 questions reflecting on the previous 12 months:
 - Are you short of breath during exercise or other physical exertion?
 - Do you wheeze after exercise or other physical exertion?
 - Do you cough after exercise or other physical exertion?
6. **Concurrent Anti-Asthma Therapy:** Subjects must be taking low- to moderate-dose inhaled steroids for 12 weeks prior to Visit 1 in order to participate with no change in dose for the 4 weeks prior to Visit 1. Example dosages considered appropriate for study participation are outlined in the SRM.
7. **Gender:** Subjects may be male or an eligible female.

A female is eligible to enter and participate in the study if she is of:

Non-child bearing potential (i.e., physiologically incapable of becoming pregnant, including any female who is post-menopausal or surgically sterile). Surgically sterile females are defined as those with a documented hysterectomy

and/or bilateral oophorectomy or tubal ligation. Post-menopausal females are defined as being amenorrhoeic for greater than 1 year with an appropriate clinical profile, e.g., age appropriate, > 45 years, in the absence of hormone replacement therapy.

OR

Child bearing potential, has a negative pregnancy test at screening, and agrees to acceptable contraceptive methods approved in their local country, when used consistently and correctly (i.e., in accordance with the approved product label and the instructions of the physician for the duration of the study – screening to follow-up contact). See [Appendix 5](#).

8. **Albuterol/salbutamol Use:** All subjects must be able to replace their current short-acting beta₂-agonist (SABA) with albuterol/salbutamol, to be used only on an as-needed basis for the duration of the study. Each subject must be judged capable of withholding albuterol/salbutamol for at least 6 hours prior to performing spirometric evaluations.
9. **Physical Capacity:** Each subject must be physically able to perform the exercise challenges on a treadmill when bronchodilators have been withheld.

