8.1. Time and Events Table

Table 3 Time and Events Table

Procedures	Pre-Screen	Screen/ Run-in	Treatment Period 1			Treatment Period 2			Early Withdrawal Visit	Follow- up Phone Call
Visit/Contact	0	1	2 ¹² Randomization	3	4 ^{12, 14}	5 ¹²	6	7 ^{12, 14}		
Week		-4	0	0	2	4	4	6		7
Treatment Day		-26 to -30 days	0	1 ¹⁸	14 (-2/+2) days	28 (-2/+2) days	29 ¹⁸	42 (-2/+2) days		47 to 51 days
Written Informed Consent	X									
Genetics Consent	X ¹									
Subject Demography	X									
Medical History (including CV)		X								
Disease (Asthma) History		X								
Medication History	X	X								
Smoking history/status		X								
Inclusion/Exclusion Criteria		X								
Evidence of EIB		X								
Efficacy Assessments										
Spirometry (full FEV ₁ and FVC)		X	X ²	X ²	X ²	X	X ²	X ²	X	
Exercise Challenge Testing (Treadmill)			X ^{3, 17}	X ⁴	X ⁵		X ⁴	X ⁵		
Post-Challenge Serial FEV ₁ Measurements			X ³	X ⁶	X ⁶		X ⁶	X ⁶		
Asthma Control Questionnaire-5			X		X	X		X	X	
Dispense SenseWear ¹⁵ accelerometer		X								
Collect SenseWear accelerometer								X	X	
Safety Assessments										
Concomitant Medication	X	X	X	X	X	X	X	X	X	X ⁷

Procedures	Pre-Screen	Screen/ Run-in	Treatment Period 1			Treatment Period 2			Early Withdrawal Visit	Follow- up Phone Call
Visit/Contact	0	1	2 ¹² Randomization	3	4 ^{12, 14}	5 ¹²	6	7 ^{12, 14}		
Week		-4	0	0	2	4	4	6		7
Treatment Day		-26 to -30 days	0	1 ¹⁸	14 (-2/+2) days	28 (-2/+2) days	29 ¹⁸	42 (-2/+2) days		47 to 51 days
Physical Examination		X								
Vital Signs		X	X ⁸	X ⁸	X ⁸	X	X ⁸	X ⁸	X	
12-lead ECG		X								
Adverse Event Assessment	X ⁹	X ⁹	X	X	X	X	X	X	X	X
Issue Medical Conditions Diary Card		X	X		X	X				
Review Medical Conditions Diary Card			X ¹⁰	X	X ¹⁰	X ¹⁰	X	X ¹⁰	X	
Laboratory Assessments										
Genetics Saliva Sample			X ¹							
Urine Pregnancy Test		X	X			X			X	X ¹³
Investigational Product										
Dispense Fluticasone Propionate		X			X					
Collect Fluticasone Propionate			X			X				
Dispense Rescue ¹⁶ Albuterol/salbutamol		X	X	X	X	X	X			
Collect Rescue Albuterol/salbutamol			X		X	X		X		
Dispense IP			X ¹¹			X				
Assess study drug compliance			X	X	X	X	X	X	X	
Collect IP					X			X	X	

1. Genetics saliva sample collected at Visit 2 (following Randomization) or at any scheduled visit thereafter. Genetics consent MUST be obtained PRIOR to collection of the Genetics sample.

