If a sample for genetic research has been collected and it is determined that the subject does not meet the entry criteria for participation in the study, then the investigator should instruct the subject that their genetic sample will be destroyed. No forms are required to complete this process as it will be completed as part of the consent and sample

reconciliation process. In this instance a sample destruction form will not be available to include in the site files.

Provision of Study Results and Confidentiality of Subject's Genetic Data

GSK may summarize the genetic research results in the clinical study report, or separately and may publish the results in scientific journals.

GSK may share genetic research data with other scientists to further scientific understanding in alignment with the informed consent. GSK does not inform the subject, family members, insurers, or employers of individual genotyping results that are not known to be relevant to the subject's medical care at the time of the study, unless required by law. This is due to the fact that the information generated from genetic studies is generally preliminary in nature, and therefore the significance and scientific validity of the results are undetermined. Further, data generated in a research laboratory may not meet regulatory requirements for inclusion in clinical care.

13.5. Appendix 5: Definition of and Procedures for Recording, Evaluating, Follow-Up and Reporting of Adverse Events

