13.5.6. Reporting of SAEs to GSK

SAE reporting to GSK via electronic data collection tool

- Primary mechanism for reporting SAEs to GSK will be the electronic data collection tool
- If the electronic system is unavailable for greater than 24 hours, the site will use the paper SAE data collection tool and fax it to the Medical Monitor
- Site will enter the serious adverse event data into the electronic system as soon as it becomes available.
- The investigator will be required to confirm review of the SAE causality by ticking the 'reviewed' box at the bottom of the eCRF page within 72 hours of submission of the SAE.
- After the study is completed at a given site, the electronic data collection tool (e.g., InForm system) will be taken off-line to prevent the entry of new data or changes to existing data
- If a site receives a report of a new SAE from a study subject or receives updated data on a previously reported SAE after the electronic data collection tool has been taken off-line, the site can report this information on a paper SAE form or to the Medical Monitor by telephone.
- Contacts for SAE receipt can be found at the beginning of this protocol on the Sponsor/Medical Monitor Contact Information page.

SAE reporting to GSK via paper CRF

- Facsimile transmission of the SAE paper CRF is the preferred method to transmit this information to the Medical Monitor
- In rare circumstances and in the absence of facsimile equipment, notification by telephone is acceptable, with a copy of the SAE data collection tool sent by overnight mail
- Initial notification via the telephone does not replace the need for the investigator to complete and sign the SAE CRF pages within the designated reporting time frames.
- Contacts for SAE receipt can be found at this beginning of the protocol on the Sponsor/Medical Monitor Contact Information page.

13.6. Appendix 6: Modified List of Highly Effective Methods for Avoiding Pregnancy in Females of Reproductive Potential (FRP) and Collection of Pregnancy Information

This list does not apply to FRP with same sex partners, when this is their preferred and usual lifestyle or for subjects who are and will continue to be abstinent from penile-vaginal intercourse on a long term and persistent basis.

- Contraceptive subdermal implant
- Intrauterine device or intrauterine system
- Oral Contraceptive, either combined or progestogen alone [Hatcher, 2007]
- Injectable progestogen [Hatcher, 2007]

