- Contraceptive vaginal ring [Hatcher, 2007]
- Percutaneous contraceptive patches [Hatcher, 2007]
- Male partner sterilization with documentation of azoospermia prior to the female subject's entry into the study, and this male is the sole partner for that subject [Hatcher, 2007].
- Male condom plus partner use of one of the contraceptive options below:
 - Contraceptive subdermal implant
 - Intrauterine device or intrauterine system
 - Oral Contraceptive, either combined or progestogen alone [Hatcher, 2007]
Injectable progestogen [Hatcher, 2007]
 - Contraceptive vaginal ring [Hatcher, 2007]
 - Percutaneous contraceptive patches [Hatcher, 2007]

This is an all inclusive list of those methods that meet the GSK definition of highly effective: having a failure rate of less than 1% per year when used consistently and, correctly and, when applicable, in accordance with the product label. For non-product methods (e.g. male sterility), the investigator determines what is consistent and correct use. The GSK definition is based on the definition provided by the ICH [ICH, M3 (R2) 2009].

The investigator is responsible for ensuring that subjects understand how to properly use these methods of contraception.

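### Inclusion criterion 7 asks only for undefined acceptable contraception and cites the adverse-event appendix, while Section 5.6.1 requires a highly effective method and the list of those methods sits in Appendix 6, which no eligibility criterion cites

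*Protocol*

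**What the plan says.** **Eligibility.** Criterion 7 in Protocol Section 6.1.1 admits two groups of women. The first is women of non-child-bearing potential, which includes the surgically sterile and the post-menopausal. The second is women of child-bearing potential who have a negative screening test and "agrees to acceptable contraceptive methods approved in their local country, when used consistently and correctly". The criterion ends by sending the reader to Appendix 5, whose title is "Appendix 5: Definition of and Procedures for Recording, Evaluating, Follow-Up and Reporting of Adverse Events".

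**Risk mitigation.** Section 5.6.1 records that neither FF/VI nor its components have been studied in pregnant women. Under the mitigation for that risk it states: "Female subjects must be postmenopausal or using a highly effective method for avoidance of pregnancy while in this study".

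**The list.** Appendix 6 (Section 13.6) names the qualifying methods, sets the threshold at a failure rate below 1% per year, and closes the list: "This is an all inclusive list of those methods that meet the GSK definition of highly effective". It exempts women with same-sex partners and women who are abstinent long term.

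**Pregnancy testing.** For enrolled women of child-bearing potential, Section 5.6.1 says "a urine pregnancy test will be performed at Screening, randomization, Visit 4 and at home at the Follow-Up contact". In Table 3 (Section 8.1), the row "Urine Pregnancy Test" is marked at Visits 1, 2 and 5, at Early Withdrawal and at the follow-up call. SAP Appendix 2 repeats that row.

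**The concern.** Sites enrol on Section 6. Its opening paragraphs forbid deviations from the criteria and call adherence to them essential. If the criterion is looser than the safeguard described elsewhere, the criterion decides who enters.

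The safeguard matters to the protocol's own argument. Section 5.6.1 offers it as the answer to a risk on which it has no human data, and Section 5.6.4 rests the benefit-risk conclusion on the measures taken to limit risk.

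The gap would also be hard to see afterwards. SAP Section 4.1 summarises eligibility deviations from the inclusion/exclusion page of the eCRF. A woman who meets criterion 7 as written would not be expected to appear there, whatever Section 5.6.1 says.

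**Working it through.** No sample size, power or error-rate figure is involved, so the check is a comparison of texts plus one interval.

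**1. Contraceptive standard**

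| Place | Standard | Defined? |
|---|---|---|
| Section 6.1.1, criterion 7 | Acceptable, locally approved, correctly used | No effectiveness level; refers to Appendix 5 |
| Section 5.6.1 | Postmenopausal, or a highly effective method | Not in that section |
| Appendix 6 | Closed list, failure rate below 1% per year | Yes |

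Criterion 7 and Appendix 6 both require consistent and correct use in line with the label, but only Appendix 6 sets a threshold. The two can give different answers for the same woman. For example, Appendix 6 lists the male condom only in combination with another named method. Whether a condom alone would count as acceptable under criterion 7 cannot be settled from the text; it is an assumption that some site would accept it.

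**2. Cross-reference**

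Appendix 5 contains adverse-event definitions, recording and reporting, and no contraceptive list. The list is in Appendix 6. None of the screening or randomization criteria in Sections 6.1 and 6.2 cites Appendix 6, so the one pointer that could have given acceptable a meaning leads elsewhere.

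**3. Groups of women covered**

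Criterion 7 names surgically sterile women as eligible; the Section 5.6.1 sentence does not mention them. Appendix 6 exempts two groups on which criterion 7 is silent. The three passages do not describe the same population.

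**4. Pregnancy-test visit**

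- Section 5.6.1: screening, randomization, Visit 4, follow-up.
- Table 3, read by column: Visits 1, 2 and 5, Early Withdrawal, follow-up. Visit 4 is blank.
- Visit 5 is also the visit of the first Period 2 dose (Section 8.3.3.5).
- Visit windows in Table 3: Visit 4 is Day 14 ± 2, so Days 12 to 16; Visit 5 is Day 28 ± 2, so Days 26 to 30.
- Interval from Visit 4 to Visit 5: nominally 28 − 14 = 14 days; at the extremes 26 − 16 = 10 and 30 − 12 = 18 days.

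That interval would separate the last test from the Period 2 dose only at a site that followed Section 5.6.1 and ignored Table 3. Under Table 3, test and dose fall at the same visit.

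**5. Reach into the analysis**

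SAP Appendix 1 lists the eligibility failures that remove a subject from the Per Protocol population. Inclusion criterion 7 and the pregnancy exclusions are not among them. No analysis set, endpoint or test depends on this point.

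**The case against.** The strongest reply is that these are editing slips. Appendix 6 is the only contraception appendix, it is titled as such in the contents, and its wording on correct use is close to that of criterion 7. A reader would guess that one digit in the cross-reference is wrong, and with that digit corrected a site would reach the list. This explains the error, but it does not fully repair the criterion: acceptable and locally approved would still stand beside a reference to highly effective methods, with nothing to say that the list is binding.

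Several stronger readings are tempting, and the documents do not support them:

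- *That criterion 7 accepts any locally approved method.* It says acceptable, which is undefined but is not the same as any.
- *That Section 5.6.1 itself imposes the closed list.* It requires a highly effective method; the list is in Appendix 6.
- *That Section 5.6.1 shuts out surgically sterile women.* Its bullets are introduced as reflecting the protocol, and criterion 7 expressly admits these women. This is a wording gap.
- *That every woman of child-bearing potential is affected.* A woman already using a method in Appendix 6 satisfies all three passages.
- *That the Visit 4/Visit 5 conflict would re-expose pregnant women.* Section 8 makes Table 3 the source of exact timing and requires adherence to it. Table 3 tests at the Period 2 dosing visit, and any positive test means withdrawal (Section 6.4.1). Pregnancy is also an exclusion at screening (Section 6.1.2) and at Visit 2 (Section 6.2.2). Each woman receives FF/VI in one period only (Table 2). The superseded schedule reproduced in Appendix 8 had its test at a Visit 4 that was then the Day 28 start of Period 2, so the Section 5.6.1 entry looks like a number not updated when visits were renumbered.

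One reservation remains on the last item: no passage states that the Visit 5 test must be read before the Visit 5 dose.

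**Conclusion.** The contraception contradiction stands. A site that follows criterion 7 exactly could enrol a woman whose method is outside Appendix 6, and so outside the protection that Section 5.6.1 offers against fetal risk. This assumes that at least one locally approved method that an investigator would call acceptable is absent from the list; the documents neither confirm nor exclude that.

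The size cannot be computed. The documents plan for 66 randomized subjects but give no expected number of women and no distribution of contraceptive methods. The number affected lies between zero and the number of enrolled women of child-bearing potential.

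The pregnancy-test discrepancy is real but secondary, because Section 8 already says which source sets the timing.

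This is a matter of subject protection and internal consistency. Sample size, error rate, power and the planned analyses are untouched. It should be corrected, and the correction is cheap.

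**What to change.** 1. Change the cross-reference in criterion 7 from Appendix 5 to the appendix that holds the contraceptive list, Appendix 6.
2. Reconcile criterion 7, the Section 5.6.1 row on fetal risk and Appendix 6 to one stated standard that covers the same groups of women, including the surgically sterile and the groups that Appendix 6 exempts. The sponsor must decide which standard applies; this review does not.
3. Reconcile the mid-study pregnancy-test visit between Section 5.6.1 and Table 3. SAP Appendix 2 now matches Table 3 and would need a change only if Table 3 changes. State the order of test and dosing at that visit while the text is open.

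The cost is a few words in one criterion, one risk-table cell and possibly one appendix, made through a protocol amendment. Nothing is added to the analysis. Depending on the standard the sponsor settles on, eligibility may become narrower or simply clearer for some women, and sites would need to be told.
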